3.3.3 Safety Variables

Safety variables include:

- Determination of DLT, MTD and RP2D
- Incidence of TEAEs:

TEAEs are defined as any AE occurring or worsening in severity after the administration of study drug. TEAEs will be categorized as:

- Relationship to entinostat
- Relationship to avelumab
- Severity/Grade according to National Cancer Institute Terminology Criteria for Adverse Events (NCI CTCAE) Version 4.03
- Action with respect to entinostat
- Action with respect to avelumab
- Seriousness and outcome

- Change in chemistry and hematology parameters from baseline to minimum and maximum post-baseline values, average post-baseline value, and last post-baseline value
- Shifts in chemistry and hematology parameters from baseline to worst post-baseline in CTCAE toxicity grade
- Shifts in chemistry and hematology parameters outside the laboratory normal range from baseline to maximum increase and/or decrease, and last post-baseline value
- Change from baseline in vital signs and weight at each post-baseline time point
- Change from baseline in 12-lead ECG parameters at each post-baseline time point
- Change from baseline in ECOG at each post-baseline time point

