with radiographic progression only, as defined by RECIST 1.1, should continue on study treatment until unequivocal PD is determined as defined by irRECIST, at the discretion of the investigator. After study treatment discontinuation, patients will complete an End of Treatment (EOT) visit within 7 days after the last study drug dose and 3 Safety Follow-up visits (30, 60 and 90 days [\pm 7 days] after the EOT visit). The 60-day Safety Follow-up will be conducted via telephone in the absence of an ongoing toxicity that requires an office assessment (per Investigator's judgement and standard of care). Patients with ongoing toxicities will be followed more frequently per the Investigator's clinical judgement and standard of care. For example, Grade 3 or higher laboratory toxicities will be assessed at least weekly until resolution to Grade 2 or baseline grade. Entinostat and avelumab related toxicities will be managed as outlined in Protocol Section 9.10.1. The 90-day visit may also be conducted via telephone in the absence of an ongoing toxicity that requires an office assessment (per Investigator's judgement and standard of care), given that the patient's 90-day thyroid function tests are assessed locally.

After completion of the 30-day (\pm 7 days) Safety Follow-up visit, patients who have not experienced PD will continue to be followed every 6 weeks for a clinic visit and radiological imaging until unequivocal PD or until study Week 36, whichever occurs first. If PD has not been documented at Week 36, patients will be followed every 8 weeks for radiological imaging until unequivocal PD, death, or end of the study, whichever occurs first. Following documentation of PD, patients will be contacted every 3 months for documentation of survival status and post-study therapies until death or closure of the study by the Sponsor.

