3.1.4 Handling of Missing/Incomplete Values

Unless otherwise specified, missing data will not be imputed. For AE start dates, the first algorithm described below will be used to determine treatment emergence. For incomplete dates of diagnosis, the second algorithm described below will be used to determine the incomplete date if the day and/or month is missing.

Algorithm for Imputation of Incomplete/Missing Adverse Event Start Dates

Case 1:

if year portion of AE start date = missing then missing AE start date = dose date;

Case 2:

if year portion of AE start date = year portion of dose date
then do;

if month portion of AE start date = missing

then missing AE start date = dose date;

else if month portion of AE start date = month portion of dose date

then missing AE start date = dose date;

else if month portion of AE start date \neq month portion of dose date

then missing AE start date = mdy(AE start month, 1, AE start year);

end;

Case 3:

If year portion of AE start date $>$ year portion of dose date, then AE is treatment-emergent.

Algorithm for Imputation of Incomplete/Missing Date of Diagnosis

If the date of diagnosis is missing the day and/or month, the following algorithm will be used.

Case 1:

For cases where day and month are unknown or missing, the day and month will be set to June 30 with the known year, provided that the resulting date is before treatment start date. Otherwise, one day prior to treatment start date (treatment start date – 1) will be used.

Case 2:

For cases where only the day is unknown or missing, the day will be set to 15 with the non-missing month and year, provided the resulting date is before the treatment start date. Otherwise, one day prior to the treatment start date (treatment start date – 1) will be used.

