To supplement the above analysis of OS, a summary of the anti-cancer therapies, and interventions received following the discontinuation of study treatment, will be provided. Such therapies will be collected during the scheduled post-treatment, follow-up assessments. The therapies will be summarized by treatment arm and will be classified as chemotherapy, hormonal therapy, radiation, surgery, maintenance or other.

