3.10.1 Adverse Events

An AE is defined as any untoward medical occurrence in a patient or clinical investigation patient administered a pharmaceutical product, and that does not necessarily have a causal relationship with this treatment. An AE can therefore be any unfavorable and unintended sign (including an abnormal laboratory finding), symptom, or disease, temporally associated with the use of a medicinal (investigational) product, whether or not the AE is related to the medicinal (investigational) product. The term also covers laboratory findings or results of other diagnostic procedures that are considered to be clinically relevant as determined by the Investigator.

Analyses of AEs will be based on the principle of treatment emergence. Treatment-emergent AEs are defined as having onset after study drug dosing or a sign, symptom, or diagnosis that worsens after study drug dosing. Henceforth, whenever an analysis or summary of AEs is mentioned, it is intended that this is in reference to TEAEs, unless it is stated otherwise.

If AE start dates are completely missing or partially missing, the date imputation rules described previously in [Section 3.1.4](#) will be applied for the determination of treatment-emergence. This algorithm will be used only if the end date of the AE (if reported) indicates the event was not resolved before the first administration of study drug. Imputed AE dates will not be used to calculate the duration of AE episodes.

All AEs will be coded according to System Organ Class (SOC) and Preferred Term

(PT) using the Medical Dictionary for Regulatory Activities (MedDRA) dictionary (Version 19.0 or later).

For the escalation phase, the observed DLT rate in each dose cohort will be calculated by the crude proportion of patients who experienced DLT with a 2-sided, 95% exact binomial CI.

A summary of AEs, including incidences of:

- AEs
- SAEs
- AEs related to entinostat (“possibly related” or “related”)
- AEs related to avelumab (“possibly related” or “related”)
- AEs related to any study drug
- SAEs related to entinostat, avelumab, or both
- AEs leading to dose modification of entinostat, avelumab, or both
- AEs leading to discontinuation of entinostat, avelumab, or both
- AEs with a fatal outcome
- AEs with a CTCAE severity grade of Grade 3 or greater
- AEs with CTCAE severity of Grade 3 or greater related to entinostat, avelumab, or both

will be presented by dose cohort in Phase 1 and by treatment arm in Phase 2.

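### The TEAE definition has a start but no end, so events arising under next-line cancer therapy during safety follow-up can be counted as treatment-emergent; several laboratory summaries are also open-ended

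*SAP*

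**What the plan says.** The SAP defines treatment emergence twice. Section 3.3.3: "TEAEs are defined as any AE occurring or worsening in severity after the administration of study drug". Section 3.10.1: "Treatment-emergent AEs are defined as having onset after study drug dosing or a sign, symptom, or diagnosis that worsens after study drug dosing". Section 3.10.1 adds that every AE summary means TEAEs unless stated otherwise.

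The rule for incomplete AE start dates in Section 3.1.4 has no upper limit either. In Case 3, an event whose start year is later than the year of dosing is settled with the words "then AE is treatment-emergent".

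Section 2.3 places the End of Treatment (EOT) visit "within 7 days after the last study drug dose and 3 Safety Follow-up visits (30, 60 and 90 days" after EOT, each with a 7-day tolerance. Section 2.3.9 lists AE and SAE recording, hematology and chemistry among the assessments at EOT and the Safety Follow-up visits, and refers to Protocol Table 1-1 for detail.

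For laboratory data, Section 3.3.3 lists "Shifts in chemistry and hematology parameters from baseline to worst post-baseline in CTCAE toxicity grade". Section 3.10.2 instead takes the maximum shift against the normal range over the period of study treatment, and says that grade shifts are analysed similarly.

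On later cancer therapies, Section 3.8 (Overall Survival) says "Such therapies will be collected during the scheduled post-treatment, follow-up assessments". PFS Sensitivity Analyses 2 and 3 use their start dates. No safety rule does.

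**The concern.** The safety objective concerns the tolerability of entinostat with avelumab. An event caused by the next line of treatment says nothing about that, yet a window without an end admits it.

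Take a patient whose last dose is at Week 12, who then starts chemotherapy and has Grade 4 neutropenia reported as an AE at Week 18. The event is 42 days after last dose and meets both definitions. It would enter the Phase 2 tables by maximum severity (14.4.3) and Grade 3 or higher (14.4.5.1) and, if serious, 14.4.7.1, under her treatment arm.

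If such events are about as frequent in both arms, they raise both rates and pull them together, which can mask a real difference. Adjusting for time on treatment would not remove them. If the window is left open now, it will have to be chosen at reporting, when the data may already be known.

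**Working it through.** The SAP states no figure on this point, so there is none to reproduce. The check is of the text, followed by a scale calculation.

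**Does any rule close the window?**
- TEAE definitions (3.3.3, 3.10.1): start only.
- Date imputation (3.1.4, Case 3): no upper limit.
- Section 2.2.2: a limit of 30 days after last dose, attached by its grammar to deaths.
- New anti-cancer therapy: used for PFS (Section 3.8), in no safety rule.

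**Length of AE recording after last dose** (Section 2.3)
- EOT at up to 7 days, plus 90 days: 7 + 90 = 97 days, or 97 / 30.4375 = 3.19 months.
- With the 7-day tolerance on the last visit: 104 days at most.

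**Share of AE observation that is off treatment**

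Formula: share = 97 / (97 + d), where d is time on treatment in days. The SAP gives no treatment-time distribution, so I take its assumed median PFS (Section 2.3.1) as a stand-in, at 30.4375 days per month (Section 3.8).

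| Arm and scenario | Median (months) | d (days) | Share |
|---|---|---|---|
| Control, low | 3 | 91.3 | 97 / 188.3 = 52% |
| Control, high | 4 | 121.8 | 97 / 218.8 = 44% |
| Entinostat, low | 5.25 | 159.8 | 97 / 256.8 = 38% |
| Entinostat, high | 7 | 213.1 | 97 / 310.1 = 31% |

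Treatment may continue past RECIST 1.1 progression while confirmation is awaited (Section 2.3.6). Adding 6 weeks (42 days) to d gives, at the extremes, 97 / (97 + 91.3 + 42) = 42% and 97 / (97 + 213.1 + 42) = 28%.

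These are shares of all off-treatment time. The part that follows a new therapy cannot be derived, because the SAP gives no distribution of its start times.

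**Direction of the effect**

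Let p be the on-treatment event rate in an arm, and q the chance of a carried-over event, assumed equal in both arms and independent of earlier events. The reported rate is p + q(1 − p), so the arm difference is multiplied by (1 − q). Purely as an assumed illustration, a true 15-point difference would fall to 13.5 points at q = 10% and 10.5 points at q = 30%. None of these inputs comes from the SAP.

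**Laboratory data**
- Grade shifts: Section 3.3.3 counts the worst value after baseline with no end; Section 3.10.2, by reference to the normal-range shifts, points to the treatment period. The two differ, and the treatment period is not given in days.
- Minimum, maximum, average and last post-baseline values (3.3.3, 3.10.2): no end in either section.

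**The case against.** **Treatment-emergent does not mean drug-caused.** A reader might infer that next-line toxicity is reported as study-drug toxicity. The documents do not support that. Sections 3.10.1 and 6.1 tabulate events related to entinostat, to avelumab and to any study drug separately, including related Grade 3 or higher and related serious events. An event judged unrelated stays out of those tables. This stands, but the all-causality tables are also main safety outputs, and they have no such filter.

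**Laboratory grade shifts are not simply unbounded.** A reader of Section 3.3.3 alone might infer that worst grades run to the end of follow-up. Section 3.10.2 points the other way. Few late values may exist in any case: the 60-day visit is by telephone unless an ongoing toxicity needs an office visit, and the 90-day visit may be too, with only thyroid tests named. This stands, and narrows the laboratory point to the mismatch and the open-ended summaries.

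**The protocol may stop AE collection when new therapy starts.** Possible, and the protocol is not at hand. But the SAP defines the TEAE itself, twice, and neither states nor cites such a limit.

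**The percentages do not measure the defect.** Correct: they bound the opportunity, not the contamination.

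**Cutting at new therapy has its own cost.** On the SAP's hypothesis control patients progress sooner, so the cut may shorten their AE observation more, whereas the present follow-up schedule is the same for both arms. This also stands and is met in the fix.

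**Conclusion.** The point holds for adverse events. The TEAE window is open in both definitions, AE recording is scheduled to about 97 days (at most 104) after last dose, and nothing ends the window at the start of another cancer therapy. Events under next-line treatment can therefore enter the all-causality, Grade 3 or higher and serious-event tables by arm. For laboratory data it holds only as a mismatch between Sections 3.3.3 and 3.10.2, plus summaries without an end.

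The size is not known. The 31% to 52% off-treatment share rests on taking median PFS as treatment time and falls to about 28% to 42% with 6 further weeks of treatment. The fraction of it spent under new therapy, and any dilution of the arm difference, are assumptions. The primary PFS analysis and the other efficacy tests are not affected. The matter is worth settling before unblinding because the safety tables by arm depend on it.

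**What to change.** 1. In Sections 3.3.3 and 3.10.1, use one definition: an AE with onset or worsening from first dose to the earlier of the 90-day Safety Follow-up visit and the day before the first new anti-cancer therapy, plus any later AE judged related to study drug. The last clause keeps related AEs a subset of TEAEs, as Section 3.10.1 requires.
2. Bring Case 3 of the date rule in Section 3.1.4 under the same end date.
3. Apply the same date cut to all post-baseline laboratory summaries, and reconcile Section 3.3.3 with Section 3.10.2 so that grade shifts have one stated window.
4. Keep the excluded later events in the listings.
5. Report the length of the AE window by arm.

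The cost is a few sentences and a date comparison; the therapy start dates are already needed for PFS Sensitivity Analyses 2 and 3. No assessment or patient management changes. The downside is that unrelated events after new therapy appear only in listings, and that observation may be shortened more in the arm that progresses sooner, which item 5 makes visible.

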3.3.4 Exploratory Variables

3.4 Disposition and Evaluability

3.4.1 Disposition

The number and percentage of patients who were screened, enrolled, dosed, and withdrew prior to receiving a dose (including reasons for not completing dosing), the number of cycles on treatment, the reason for screen failure, the reasons for discontinuation of each study treatment, the reason for discontinuation of the study, will be presented by dose cohort in Phase 1 and by treatment arm in Phase 2.

3.4.2 Protocol Deviations

Protocol deviations will be presented in a patient listing.

3.5 Demographics and Baseline Characteristics

3.5.1 Demographics

Demographics will be summarized by dose cohort for the Safety Analysis Set (Phase 1 only) and will be summarized by treatment arm for the FAS. Frequency statistics will be presented for sex, race, ethnicity, age group, and ECOG performance status at baseline. Summary statistics will be presented for age, weight (kg), height (cm), and body surface area (m^2).

Body surface area will be calculated using the Mosteller formula:

$$\text{Body surface area} = \sqrt{\frac{\text{height (cm)} \times \text{weight (kg)}}{3600}}$$

All demographic data will be presented in patient listings.

3.5.2 Ovarian Cancer Disease History

The following baseline disease characteristics variables will be summarized for the FAS:

- Time since initial diagnosis
- Disease stage at initial diagnosis

- Histopathological grade at initial diagnosis
- Time since diagnosis of advanced or metastatic ovarian cancer
- Metastatic sites

Disease history, including prior anti-cancer therapies, surgeries, and radiotherapy, will be summarized by dose cohort and by treatment arm for the Safety Analysis Set (Phase 1 only) and for the FAS, respectively. Frequency statistics will be presented for ECOG performance status, primary tumor location, [REDACTED], and disease status at enrollment. Summary statistics will be presented for years since diagnosis.

If the date of diagnosis is missing the day and/or month, the algorithm specified in [Section 3.1.4](#) for incomplete dates will be used to determine the date and time since the study start.

All ovarian cancer disease history data will be presented in patient listings.

3.5.3 Medical History, Prior Medications, and Physical Exam

Data regarding medical history, prior medications, and clinically significant findings from the physical exam will be presented in patient listings for the Safety Analysis Set (Phase 1 only) and for the FAS.

3.6 Concomitant Medications

Any medication reported on the appropriate post treatment form (Concomitant Medications) will be considered concomitant.

All medications will be coded using the World Health Organization (WHO) Drug Dictionary (September 2016). The number and percentage of patients taking each concomitant medication will be presented by dose cohort (Phase 1) and treatment arm (Phase 2) for the Safety Analysis Set. All medication data will be listed individually and summarized by anatomical therapeutic class and generic name.

3.7 Treatment Exposure

The overall duration of study drug administration (in days) and the total number of cycles started will be tabulated for each patient and summarized for each study phase. The average dose administered and cumulative dose of entinostat administered (in mg)

will be calculated. These data will be further summarized by calculating the mean, standard deviation, median, and range of these values. The average proportion of the planned doses of study drug will be calculated for all patients. Similar analyses will be performed for avelumab administration (in mg/kg). The number and proportion of patients with one or more dosage modification (i.e., reduction or delay) of each study drug will be tabulated along with the reasons for dosage modification. The primary reason for study drug discontinuation will be tabulated in a similar manner. All treatment exposure data will be presented in patient listings for the Safety Analysis Set.

3.8 Efficacy Analysis

Efficacy analyses will be performed using the FAS and, where appropriate, the Per-Protocol Set. The efficacy outcomes for the patients enrolled in the Phase 1b portion of the study will be reported in listing format and may be summarized in a descriptive manner using the analysis conventions described below, as appropriate. The primary analysis of PFS will be based on the first 97 PFS failures. The calendar date of the 97th event will serve as the data cutoff date for the primary analysis. The primary analysis of the secondary endpoints, exploratory endpoints, and safety will occur at the time of the primary PFS analysis. An interim analysis is planned after 65 PFS failures (67% of total events) observed in Phase 2. The calendar date of the 65th event will serve as the data cutoff date for the interim analysis. With the exception of PFS, all hypothesis testing will be assessed using a one-sided significance level of 0.1. The Lan-DeMets alpha spending function with an O'Brien-Fleming type boundary will be used to control type I error for multiple testing of PFS. The details of alpha spending are described in [Section 2.3.2](#).

Progression-free Survival

The primary efficacy endpoint is duration of PFS, defined as the number of months from randomization to PD or death due to any cause, whichever occurs first. Disease assessments will continue until PD, even after the originally assigned study treatment is discontinued. For purposes of analysis, 1 month is considered 30.4375 days. The duration of PFS as determined by RECIST 1.1 ([Eisenhauer 2009](#)) and irRECIST ([Seymour 2017](#)) will be summarized descriptively using the Kaplan-Meier method

(Kaplan 1958). Inferential comparisons between treatment arms will be made using the log rank test, stratifying on the randomization stratification factors. The Cox proportional hazard model (Cox 1972) with treatment as a factor, stratified by the stratification factors used in randomization, will be used to estimate the HR for treatment effect and corresponding 95% CI, without any other covariate adjustment. The corresponding results without stratification will be reported as supplemental analyses. The adequacy of the Cox model will be evaluated, including an assessment of the proportional hazards assumption (Therneau 2000).

For the interim and primary analyses, the date of progression or censoring for PFS will be determined according to the conventions listed in [Table 3-1](#).

All patients are to be followed for disease progression according to the protocol-specified schedule even after a non-protocol, anti-cancer therapy is started. For the primary analysis of PFS, documented disease progression (or death without prior disease progression) occurring after the start of such therapy will be considered as a PFS event.

Table 3-1. Date of Progression or Censoring for Progression-free Survival

Situation	Date of Progression or Censoring	Outcome
Documented disease progression	Date of disease assessment showing documented disease progression	Progressed
Death without documented progression	Date of death	Progressed
No baseline disease assessments	Date of randomization	Censored
No post-baseline assessment and no death	Date of randomization	Censored
Death or documented progression after more than one missed consecutive post-baseline disease assessment	Date of last disease assessment visit without documentation of disease progression that is before the missed visit or date of randomization, whichever is later	Censored
Alive and without documentation of disease progression	Date of last disease assessment	Censored
Patient lost to follow-up (or withdrew consent from study participation) before documented	Date of last disease assessment	Censored

progression or death		
----------------------	--	--

Sensitivity Analyses of Progression-free Survival

Sensitivity analyses will be undertaken for calculation of the primary endpoint in order to evaluate the robustness of the analysis by changing one or more of the censoring rules stated in the primary analysis ([Table 3-1](#)). The following sensitivity analyses will be performed for PFS:

Progression-free Survival Sensitivity Analysis 1 (forward-dating PFS assessment time)

A main source of potential bias for the PFS endpoint arises from differences between the actual and observed date of disease progression, particularly if the difference is systematically related to the patient's treatment arm. Deviations from scheduled assessment times may be due to 1) AEs causing delays on one treatment arm, 2) more frequent assessments in one treatment arm because of toxicity or worsening symptoms, 3) delay in assessments because patients are doing well.

To address the above concerns, analyses will be performed to identify asymmetry between treatment arms for the frequency of missed disease assessment times, and deviations between the actual and scheduled assessment times. Descriptive statistics of frequency of missed scheduled assessment, and deviation between actual and scheduled assessment time, will be summarized by treatment arm for FAS.

In addition to the above, the PFS analysis also will be re-run with the following modifications made to the progression and censoring dates for the following cases:

- For patients with disease progression that was documented between two scheduled disease assessments, the date of disease progression will be moved forward to the date of the next planned disease assessment.
- For patients without disease progression, and whose last disease assessment was between two scheduled assessments, the censoring date will be moved forward to the date of the next planned disease assessment.

The definition of PFS for this sensitivity analysis is presented in [Table 3-2](#). Those items that differ from [Table 3-1](#) are underlined.

Progression-free Survival Sensitivity Analysis 2 (Subsequent anti-cancer therapy as

a PFS event)

As noted previously, disease assessments will continue until disease progression, even after non-protocol anti-cancer therapy is started. It's anticipated that some patients may receive subsequent anti-cancer therapy prior to documentation of PD.

To assess the impact of subsequent anti-cancer therapy on the primary PFS analysis, the start of a new anti-cancer therapy will be considered as a PFS event in this sensitivity analysis. The start date of the new anti-cancer therapy will serve as the progression date.

The definition of PFS for sensitivity analysis is presented in [Table 3-3](#). Those items that differ from [Table 3-1](#) are underlined.

Progression-free Survival Sensitivity Analysis 3 (Censoring for subsequent anti-cancer therapy)

Another sensitivity analysis will be conducted to further evaluate the impact of subsequent anti-cancer therapy on the primary PFS analysis. For patients who started a new anti-cancer therapy prior to progression, including any post-discontinuation treatment therapy, PFS will be censored at the date of the last disease assessment before the new therapy was started, regardless of whether or not this patient subsequently experienced PD or death. The definition of PFS for this sensitivity analysis is presented in [Table 3-4](#). Those items that differ from [Table 3-1](#) are underlined.

Table 3-2. Progression-free Survival Sensitivity Analysis 1

Situation	Date of Progression or Censoring	Outcome
Documented disease progression	Date of disease assessment showing documented disease progression	Progressed
Death without documented progression	Date of death	Progressed
No baseline disease assessments	Date of randomization	Censored
No post-baseline assessment and no death	Date of randomization	Censored
Death or documented progression after more than one missed consecutive post-baseline disease assessment	Date of last disease assessment visit without documentation of disease progression that is before the missed visit or date of randomization,	Censored

	whichever is later	
Alive and without documentation of disease progression	Date of last disease assessment	Censored
Patient lost to follow-up (or withdrew consent from study participation) before documented progression or death	Date of last disease assessment	Censored
Documented disease progression between two scheduled disease assessments	Date of next scheduled disease assessment	Progressed
Alive and without documentation of disease progression and last disease assessment was between two scheduled assessments	Date of next scheduled disease assessment	Censored

Note: items that differ from [Table 3-1](#) are underlined.

Table 3-3. Progression-free Survival Sensitivity Analysis 2

Situation	Date of Progression or Censoring	Outcome
Documented disease progression	Date of disease assessment showing documented disease progression	Progressed
Death without documented progression	Date of death	Progressed
No baseline disease assessments	Date of randomization	Censored
No post-baseline assessment and no death	Date of randomization	Censored
Death or documented progression after more than one missed consecutive post-baseline disease assessment	Date of last disease assessment visit without documentation of disease progression that is before the missed visit or date of randomization, whichever is later	Censored
Alive and without documentation of disease progression	Date of last disease assessment	Censored
Patient lost to follow-up (or withdrew consent from study participation) before documented progression or death	Date of last disease assessment	Censored
New anti-cancer treatment started	Date of the new anti-cancer treatment started	Progressed

Note: items that differ from [Table 3-1](#) are underlined.

Table 3-4. Progression-free Survival Sensitivity Analysis 3

Situation	Date of Progression or Censoring	Outcome
Documented disease progression	Date of disease assessment showing documented disease progression	Progressed
Death without documented progression	Date of death	Progressed
No baseline disease assessments	Date of randomization	Censored
No post-baseline assessment and no death	Date of randomization	Censored
Death or documented progression after more than one missed consecutive post-baseline disease assessment	Date of last disease assessment visit without documentation of disease progression that is before the missed visit or date of randomization, whichever is later	Censored
Alive and without documentation of disease progression	Date of last disease assessment	Censored
Patient lost to follow-up (or withdrew consent from study participation) before documented progression or death	Date of last disease assessment	Censored
New anti-cancer treatment started	Date of last disease assessment visit without documentation of disease progression that is before the start of new anti-cancer treatment	Censored

Note: items that differ from [Table 3-1](#) are underlined.

Objective Response Rate

Objective response rate will be estimated based on the crude proportion of patients in each treatment arm whose best overall response during the course of study treatment is CR or PR. Tumor response will be assessed using RECIST 1.1 and irRECIST, as outlined in Protocol Section 5.1. Approximate 95% confidence intervals (CIs) will be calculated by treatment arm for the true ORR. The inferential comparison of the observed ORRs will be made using the Cochran-Mantel-Haenszel chi-square test, stratified by the randomization stratification factor(s). The corresponding results without stratification will be reported as supplemental analyses.

Duration of Response and Time to Response

Duration of response will be calculated for patients who achieve CR or PR. For such patients, DOR is defined as the number of months from the start date of the PR or CR (whichever response occurs first and subsequently confirmed), to the first date that recurrent disease or PD is documented. The same analysis will be repeated for patients who achieve immune-related CR (irCR) or immune-related PR (irPR). The date of progression or censoring for DOR will be determined according to the conventions listed [Table 3-5](#). These conventions are based on the May 2007 FDA Guidance for Industry, ‘*Clinical Trial Endpoints for the Approval of Cancer Drugs and Biologics*’. DOR will be summarized descriptively using the Kaplan-Meier method.

Table 3-5. Date of Progression or Censoring for Duration of Response

Situation	Date of Progression or Censoring	Outcome
Documented disease progression	Date of disease assessment showing documented disease progression	Progressed
Death without documented progression	Date of death	Progressed
Death or progression after more than one missed disease assessment	Date of last disease assessment visit without documentation of disease progression that is before the missed visit	Censored
Alive and without documentation of disease progression	Date of last disease assessment	Censored

Time to response will be calculated for patients who achieve a CR or PR. For such patients, TTR is defined as the number of months from the randomization date to the first date the patient achieved a PR or CR (whichever response occurs first and was subsequently confirmed). The same analysis will be repeated for patients who achieve irCR or irPR.

Clinical Benefit Rate

Clinical benefit rate, as determined by RECIST 1.1, will be estimated based on the crude proportion of patients in each treatment arm whose best overall response during the course of study treatment is a CR, PR, or SD lasting for at least 6 months. Stable

disease will be measured from the start date of study treatment until the criteria for PD is first met. The analysis of CBR and its duration will be based on the methods described above for ORR and DOR, respectively. Approximate 95% CIs will be calculated by treatment arm for the CBR. The comparison of the observed CBRs will be made using the Cochran-Mantel-Haenszel chi-square test, stratified by the randomization stratification factor(s). The corresponding results without stratification will be reported as supplemental analyses. Clinical benefit rate, as determined by irRECIST, will be estimated based on the crude proportion of patients in each treatment arm whose best overall response during the course of study treatment is an irCR, irPR, or irSD, lasting for at least 6 months. The analysis of CBR, based on irRECIST, will follow the same method described above.

Overall Survival

Overall survival is defined as the number of months from randomization to the date of death (due to any cause). Patients who are alive or lost to follow-up (as of the data analysis cutoff date) will be right-censored. The censoring date will be determined from the patients' date of last contact or data analysis cutoff date, whichever date occurs first. The analysis of OS will be based on the methods described above for PFS. The duration of OS will be summarized descriptively using the Kaplan-Meier method with 95% CIs, calculated using Greenwood's formula. For the primary analysis of OS, the difference in treatment effect will be tested using the stratified log rank test, stratifying on the randomization stratification factors. Estimation of the HR for treatment effect and its corresponding 95% CI will be determined using a stratified Cox proportional hazards model, without any other covariate. Homogeneity in the HRs across randomization strata will be examined by Wald's test using a two-sided significance level of 0.05.

To supplement the above analysis of OS, a summary of the anti-cancer therapies, and interventions received following the discontinuation of study treatment, will be provided. Such therapies will be collected during the scheduled post-treatment, follow-up assessments. The therapies will be summarized by treatment arm and will be classified as chemotherapy, hormonal therapy, radiation, surgery, maintenance or other.

